Background Rationale:	
Obstructive Sleep Apnea Syndrome (OSA) is a highly prevalent sleep disorder and is characterized by repeated episodes of obstruction of the sleep apnea during sleep which accompanies intermittent anxiety and sleep fragmentation. ment of this pathology with numerous serious repercussions on the health of the individual, various technologically advanced systems are being developed which aim to minimize the bulk of the sensors on the patient, increase the comfort of the examination and reduce the need for multiple hospital visits.
 
Among the recently developed systems is Soundi, a small, lightweight medical device that allows non-invasive monitoring and continuous recording of vital parameters. The results obtained so far on healthy subjects are very encouraging, but for the market introduction of SOUNDI as a certified medical device its clinical validation on patients is necessary.

Study design:	
This is a pre-marketing, single-center, prospective clinical investigation to compare the effectiveness and safety of the SOUNDI medical device compared to polysomnography in detecting parameters for the diagnosis of OSA in subjects suspected of having a sleep disorder.
 
All eligible subjects will be placed with the Sound device at the same time as a traditional polysomnography machine.
 
The signals will be acquired for approximately 8 hours during a single night with both systems simultaneously and will then be calculated, via automatic analysis software, with subsequent manual correction by a doctor expert in sleep medicine, the indices used, according to international guidelines, for the diagnosis of breathing and sleep disorders.
 
No further follow-up is planned for subjects.

Goals:	
Primary objective: Evaluate the effectiveness of the SOUNDI system in detecting parameters necessary for the diagnosis of OSA compared to polysomnography (gold standard) in subjects with suspected diagnosis of sleep disorders.
 
Secondary objectives:
 
 • Evaluate the safety and tolerability of the SOUNDI system • Evaluate the level of patient satisfaction in using the SOUNDI system.
Endpoints:	
Primary endpoint: Equivalence between the detection of parameters useful for the diagnosis of OSA using the SOUNDI system and standard polysomnographic methods.
 
Secondary endpoints:
 
 • evaluation of satisfaction with the use of SOUND I after the night of recording the parameters, by completing a questionnaire. • safety and tolerability of the SOUNDI device using it recording of adverse events.
Estimated enrollment:	50 subjects
Study population:	Adult subjects belonging to the clinical centre, to carry out a polysomnography for suspicion of a breathing disorder sleep.
Inclusion criteria and exclusion:	
Inclusion criteria:
 
 • Signature of informed consent • Patients of both sexes, of any ethnicity • Age between 20 and 70 years • Prescription, from clinical practice, to carry out a polysomnography on suspicion of a breathing disorder in sleep. 
Exclusion criteria:
 
 • Women during pregnancy • Insufficient cooperation/degree of collaboration in following the procedures required by the study • Participation in another clinical study. • Allergy to one of the materials in the device • Pacemaker users.
Procedures:	
Some data will be collected during a visit anthropometric devices will be positioned simultaneously for polysomnography:
 
 - a traditional polysomnigraph, as prescribed - the experimental Soundi device. 
During the night, at the patient's home, the following parameters will be acquired for at least 8 consecutive hours: oro-nasal flow, thoracic and abdominal respirogram, snoring, ECG, arterial oxygen saturation, body position.
 
The following morning the subject will return to the clinics to return the two systems and complete a simple satisfaction questionnaire prepared for the study.

	
Efficacy analyzes will be carried out on all patients who have completed the evaluation and whose data will be considered evaluable.
 
For each parameter, the agreement between the measurement carried out with the SOUNDI method and the one carried out with polysomnography will be evaluated using the Bland-Altman graph and the Concordance Correlation Coefficient (CCC).
 
Statistical considerations:
 
Descriptive statistics will be used to evaluate the subject's satisfaction with using SOUNDI.
 
The safety analyzes will be carried out on all patients to whom the Sound device and the polysomnography device have been applied, regardless of the validity of the data collected. The safety analyzes will be of a descriptive nature.
 
A sample of 50 analyzable patients will guarantee a power of 90% in determining six values of the parameters detected with the SOUNDI method which are in agreement with those measured by polysomnography.

Study duration:
	
The expected duration of enrollment of all subjects is approximately 6 months.
 
The expected duration of the study for the subject is a maximum of 24 hours.
 
The overall duration of the study will be 1 year.

Summary

1. Abbreviations	9
2. Operational Background	10
2.1 Rational	10
2.2 Background	10
3. Information on the medical device Pre-clinical	11
3.1 trials Trials on healthy	14
3.2 volunteers Risks and	14
3.3 benefits	15
4. Study Design Comparison	15
4.1	15
5. Objectives of the study	16
5.1 Primary objective	16
5.2 Secondary objectives	16
6. Study population Number of	16
6.1 patients Inclusion	16
6.2 criteria Exclusion	16
6.3 criteria	16
7. Study procedures	16
7.1 Compliance with Followup	17
7.2 procedures	17
8. Duration of the study	18
8.1 Interruption and withdrawal of subjects from the clinical investigation	18
8.2 Early closure or suspension of the study	18
9. Evaluation of effectiveness	19
9.1 Primary endpoint	19
9.2 Secondary endpoint	19
10. Evaluation of the safety and vigilance of the medical device	19
10.1 Recording of adverse events Definitions	19
10.2 Classification	19
10.3 of adverse events Predictable/expected	20
10.4 adverse events and effects Reporting of adverse	22
10.5 events Notification to the Competent	22
10.6 Authorities 10.7 Consequences on risk	22
analysis	23
11. Statistics	23
11.1 Effectiveness analysis	23
11.2 Securityanalysis	23
11.3 Analysis set	24
11.4 Systematic errors - bias	24
12. Medical device	24

2.1 Background

Obstructive Sleep Apnea Syndrome (OSA) is a highly prevalent sleep disorder and is characterized by repeated episodes of obstruction of the upper airways during sleep which are accompanied by intermittent anxiety and sleep fragmentation. OSA, being associated with excessive daytime sleepiness and increased cardiovascular risk, significantly increases mortality and morbidity in the affected population, constituting a public health problem. These consequences are significantly reduced by the early and appropriate implementation of specific treatments for apnea such as Continuous Positive Airway Pressure (CPAP), weight loss, surgery or mandibular advancement systems (MAD).

The diagnosis at the moment is carried out by carrying out polysomnographic tests which can be carried out at home or in a hospital environment. Polysomnography is based on the nocturnal collection of various vital parameters capable of providing an objective quantification of the number, characteristics and intensity of apneas.

The parameters that are acquired during complete polysomnographies are: Electroencephalogram (EEG), eye movements, muscle tone of the mylohyoid muscle and tibial muscles, nasal, thoracic and abdominal respirogram, body position, oximetry, Electrocardiogram (ECG).

For cardiorespiratory polysomnography, the number of parameters is smaller (nasal, thoracic and abdominal respiration, body position, oximetry, ECG).

In both cases, however, the patient must be prepared with the positioning of the sensors in the hours preceding the examination, he must keep them worn throughout the night and have them removed in the morning by expert technicians who also proceed to download the data from the memory on which they are collected during the night. Some tests are carried out at home and therefore the patient must access the hospital in the evening and one in the morning for to dismantle the equipment, or are carried out in the hospital and in this case the patient remains sleeping inside the structure.

2.2 Rational

To facilitate easier access to the diagnosis and therefore treatment of this pathology with numerous serious repercussions on the health of the individual, various technologically advanced systems are being developed which aim to minimize the bulk of the sensors on the patient, increase the comfort of the examination and reduce the need for multiple hospital visits. Among the recently developed systems is Soundi.

Soundi is a small, lightweight medical device that allows non-invasive monitoring and continuous recording of blood pressure, without the use of a cuff, and a whole series of physiological parameters including temperature, ECG, ejection fraction, blood pressure, respiratory rate, flow, oxygen saturation, apnea/hypopnea index. This innovative device can completely revolutionize the concept of monitors sleep aid, currently carried out using invasive instrumentation methods. Soundi will allow the patient, once worn, to carry out all his normal daily activities without any discomfort.

Simultaneous collection of a number of parameters using a single vital sign detection device can provide close, long-term, low-cost and shareable health status monitoring, with the potential to improve health management and quality of life, promote both early intervention and proactive care and reduce healthcare costs.

The results obtained so far on a population of healthy subjects are very encouraging (2-3-4-5), but its production and introduction on the market as a certified medical device requires its clinical validation on patients.

3. Information about the medical device

Soundi is a wearable medical device for the continuous monitoring of vital parameters capable of collecting useful information for the diagnosis and follow-up of breathing disorders in sleep.

The SOUNDI medical device is produced by the Biocubicasrl company. The measurement unit is made of plastic material (PA12 food grade), the ECG connector cover is made of food grade silicone, ECG cables (Spes Medica SpA) are made of Cu/Ag with PVC insulation and the medical double-sided adhesive (MED6364R) is made up of a double coating, thin, conformable, with transparent and moisture-resistant polyester film on both sides.

The current prototype of the Soundi device was developed on the basis of a technology patented by Biocubica (Italian patent no. 102016000052588 "Physiological monitoring device" and European patent EP3.248.541 "Physiological monitoring device") (1) and is equipped with the ability to listen, through a particular bell shape, to all the sound evidence nothing from our body and generated at different frequencies by different organs and/or muscles and tissues, and transduce them, through a series of sensors and with appropriate algorithms, into different vital signals.

Specifically, the parameters Soundi detects are:

- Temperature
- Heart rate
- ECG
- Oxygen saturation
- Respiratory rate
- Flow
- Snoring
- Nocturnal posture
- Numeropassi.

Soundi is also able to record environmental parameters in which the individual lives, in particular it detects temperature, relative humidity, pressure, CO2 equivalent, Volatile Organic Compounds (VOC) produced by human breathing (for example CO) and by the environment (for example formaldehyde).

Soundi is a small (diameter of 60 mm and height of 12 mm), lightweight, which is applied with a double-adhesive medical patch on the left hemithorax and can record the parameters over 24 hours for up to 15 consecutive days. Equipped with a rechargeable battery, it is capable of providing continuous measurement of the main physiological parameters.

Soundi is made up of the following components (Figure 1):

1. multi-sensor measuring unit (Figure 2)
2. ignition key

3. a double-adhesive medical plaster.

Figure 1. SOUNDI:1.Measurement unit;2.Ignition key;3.Double-sided medical tape.

[figure not shown]

Figure2. Image of the SOUNDI multisensor measurement unit

Soundi is supplied with the following accessories:

- 1-channel ECG cable
- USB cable to allow charging of the rechargeable battery and connection to the PC
- power supply
- software pcSOUNDIDOC.

The device will be used for full cardiorespiratory monitoring.

Being a wearable device also intended for non-hospitalized patients, SOUNDI is also intended to be used in a home environment.

The SOUNDI device records in internal memory the physiological data of the monitored person. The data is then downloaded, via USB cable, to the PC to be converted into a file with standard edf, the same format as the file returned by the standard polysomnography device.

SOUNDIDOC is the software for managing the SOUNDI device. It is a desktop software mainly composed of two sections/functionalities:

1. Examination programme
2. DownloadExam.

The recording file downloaded onto the experimenter's PC will then be analyzed with the Remlogic software already in use at the center for the analysis of polysomnographic signals.

Figure 3 shows the SOUNDI system diagram.

[figure not shown]

Figure3. SOUNDI system

Figure 4 shows the block diagram of the hardware part of the device.

[figure not shown]

Figure4. Block diagram

The SOUNDI medical device will be provided to the Investigator together with the current version of the User manual.

The Experimenter will be required to carefully read the manual before using the device so as to be aware of important information such as safety warnings, dangers, precautions, calibration, use, contraindications, maintenance and storage etc...

The SOUNDI device does not require any particular maintenance if the following conditions are met:

- o Cleaning the device: The SOUNDI device should never be immersed in any liquid. The unit should be cleaned with a neutral soap solution with a soft cloth. Never use a sharp tool to remove dirt, as it will scratch the surface.
- o Storage: The SOUNDI device must be stored in a dust-free environment, at a temperature between -25°C and +70°C and at a relative humidity of less than 93%.

The SOUNDIDOC software package will be installed by sponsor personnel on a PC indicated by the experimenter. A sufficient number of SOUNDI device samples to conduct the investigation clinic will be provided at the center.

3.1 Pre-clinical tests

The preclinical evaluation of the SOUNDI device concerned:

- verifying compliance of the SOUNDI medical device with the European Medical Device Directive using biocompatibility and electromagnetic compatibility testing
- electrical safety carried out at the MTICINTERCERT certified laboratory (annex 9 _SOUNDI_06_FT_01_Proveditipo).
- the verification and validation of the software reported in the Technical File, in the file 11_FT_01_VerificaRequisitiSW.

3.2 Tests on healthy volunteers

The results obtained so far on a population of healthy subjects are very encouraging (2-3-4-5).

Marzoratietal (2) demonstrated in a court of 20 healthy subjects that the use of Sound for non-invasive measurement of blood pressure produces results with accuracy comparable to that of a normal blood pressure monitor.

Furthermore, Marzoratietal (3) have proposed an innovative algorithm to improve the accuracy in the detection of signals recorded by Soundi during 24 hours.

Based on measurements taken in five male volunteers who had no previous signs of cardiovascular disease, Rossietal (4) suggested a robust deep learning model to improve the estimation of the variables extractable from the signals acquired by the Soundi.

Rossietal (5) used Soundi on a group of 20 healthy subjects to carry out acquisitions of physiological signals during sleep. Through an algorithm based on artificial intelligence they extracted the main parameters linked to respiratory disorders in sleep with an accuracy of approximately 97%.

3.3 Risks and benefits

The main risks associated with the use of the SOUNDI device by the subjects included in the clinical investigation are:

- Discomfort associated with positioning/removing the measurement unit using double-sided adhesive medical
- Allergic reaction to double-sided adhesive components

These risks will be minimized by the training of the personnel who will place and remove the device from the subject and by the exclusion from the study of subjects with a known allergy to the components of the double-sided adhesive.

The intrinsic risks most related to the design of the device (explosion/fire of the battery, electrocution linked to electrical leakage, emission of electromagnetic radiation, etc.) were evaluated and minimized in the design phase and verified through laboratory tests (electrical safety and electromagnetic compatibility).

The simultaneous collection of vital signs may allow for an early diagnosis of OSA in subjects suspected of having a sleep disorder.

Furthermore, the clinical validation of the SOUND I device on patients will allow the marketing of a small, handy and inexpensive device for the continuous monitoring of vital parameters, capable of collecting useful information for the early diagnosis or follow-up of breathing disorders in sleep.

4. Study design

This is a pre-marketing, single-center, prospective clinical investigation to compare the effectiveness and safety of the SOUNDI medical device compared to polysomnography in detecting parameters for the diagnosis of OSA in subjects suspected of having a sleep disorder.

The study expects to enroll 50 patients.

All patients belong to the Sleep Medicine Center of the Italian Auxological Institute IRCCS-San Luca Hospital in Milan.

After signing the informed consent, the Sound device will be placed in all eligible subjects and at the same time as a traditional polysomnography device the activation of the devices for the acquisition of the parameters will be programmed so that it begins when the subject lies down.

The signals will be acquired for approximately 8 hours during a single night with both systems simultaneously and will then be calculated, via automatic analysis software, with subsequent manual correction by a doctor expert in sleep medicine, the indices used, according to international guidelines, for the diagnosis of breathing and sleep disorders.

No further follow-up is planned for subjects.

4.1 Comparison

As a comparison to evaluate the effectiveness of the SOUND In device in detecting the parameters for the diagnosis of OS, an Embletta polysomnography machine (Natus) will be used. This device is already in use at the clinical center and will be used according to clinical practice for polysomnography.

5. Objectives of the study

5.1 Primary objective

Evaluate the effectiveness of the SOUNDI system in detecting parameters necessary for the diagnosis of OSA compared to polysomnography (gold standard) in subjects with a suspected diagnosis of sleep disorders.

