6.3 Exclusion criteria

- Women during pregnancy
- Insufficient cooperation/degree of collaboration in following the procedures required by the study
- Participation in another clinical study.
- Allergy to one of the materials in the device
- Pacemaker users.

7. Study procedures

All subjects enrolled in the study will undergo polysomnography (monitoring

nocturnal cardiorespiratory for the diagnosis of apnea in sleep) with traditional polysomnography (Embletta, Natus) according to normal clinical practice and at the same time as data acquisition with the Soundi system.

On the afternoon before the night of the evaluation, at the Sleep Medicine Service clinic, each object will be placed

- a traditional polysomnigraph, as prescribed
- the Soundi experimental device.

The patient will be instructed by the Investigator on the correct management of the devices.

During the visit, the following anthropometric data will be collected: age, Body Mass Index (BMI), neck circumference and abdomen.

Furthermore, the Experimenter will program the devices to begin recording the parameters at the moment the subject expects to recharge and continue for at least 8 consecutive hours.

During the night, at the patient's home, the following parameters will be acquired with two systems: oro-nasal flow, thoracic and abdominal respirations, snoring, ECG, arterial oxygen saturation (SaO₂), body position.

The following morning the subject will return to the clinics to return the two systems which will be detached by the medical staff. There, the subject will be asked to fill out a simple satisfaction questionnaire prepared for the study.

The signals acquired with both systems simultaneously will be processed by the software RemLogic, via automatic analysis software, with subsequent manual correction by a doctor expert in sleep medicine, the following indices used, according to international guidelines, for the diagnosis of respiratory and sleep disorders:

- Apnea Hypopnea Index (AHI) total and supine
- AHI central
- AHI obstructive
- Oxygen Desaturation Index (ODI)
- Average arterial oxygen saturation (SaO₂).
- Minimum SaO₂
- Time with SaO₂ < 90%
- Average heart rate
- Minimum heart rate
- Percentages of time spent in different body positions.

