11.1 Effectiveness analysis

The continuous variables will be reported as the mean value and standard deviation or as the median and interquartile range in the case of non-normally distributed data. Therefore, for each parameter the agreement between the measurement carried out with the SOUNDI method and the one carried out with polysomnography (gold standard) will be evaluated using the Bland-Altman graph and the Concordance Correlation Coefficient (CCC) [6]. In short, this graph represents the value of the differences of the measurements carried out with two methods differ from their average[7]. The CCC varies between -1 and 1, values between 0.61 and 0.80 indicate substantial agreement while values greater than 0.81 almost perfect agreement according to the Landis and Koch scale [8].

Descriptive statistics will be used to evaluate the subject's satisfaction with using SOUNDI.

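### The reference called polysomnography and gold standard is, by the protocol's own distinction, home cardiorespiratory polysomnography without EEG, so the claim should be named and limited accordingly

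*Protocol*

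**What the plan says.** Section 5.1 sets the primary objective as the detection by SOUNDI of parameters needed to diagnose OSA, "compared to polysomnography (gold standard) in subjects with a suspected diagnosis of sleep disorders". The synopsis says the same. Section 11.1 keeps the label for the analysis: agreement between SOUNDI and "the one carried out with polysomnography (gold standard) will be evaluated using the Bland-Altman graph" and the CCC. The primary endpoint in section 9.1 refers to standard polysomnography without saying which kind.

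Section 2.1 describes two kinds. The first: "The parameters that are acquired during complete polysomnographies are: Electroencephalogram (EEG), eye movements, muscle tone", followed by respiratory, position, oximetry and ECG signals. The second: "For cardiorespiratory polysomnography, the number of parameters is smaller (nasal, thoracic and abdominal respiration, body position, oximetry, ECG".

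Section 7 describes the study examination as monitoring that is "nocturnal cardiorespiratory for the diagnosis of apnea in sleep) with traditional polysomnography (Embletta, Natus) according to normal clinical practice". It adds: "During the night, at the patient's home, the following parameters will be acquired with two systems", namely "oro-nasal flow, thoracic and abdominal respirations, snoring, ECG, arterial oxygen saturation (SaO₂), body position".

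Section 7.1 defines a valid test by at least four hours of sleep. Section 11.3 excludes measurements that last less than four hours because of malfunction or malposition of the device. No section states the time base of AHI or ODI.

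**The concern.** The sections that carry the claim (synopsis, 5.1, 9.1, 11.1) drop a distinction that the background section draws. A reader of the objective, endpoint and analysis alone would not learn that the reference is the reduced test.

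This matters because the study is a pre-marketing validation. As worded, a high CCC would be reported as agreement with a gold standard, whereas the data can show agreement only with cardiorespiratory polysomnography recorded at home. Both recordings lack the signals that separate sleep from wake in the complete test, and both pass through the same RemLogic analysis. An error that both share on that account cannot show in a comparison of one with the other.

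The same gap makes one rule unworkable as written: the listed signals do not measure hours of sleep, yet section 7.1 makes validity depend on them.

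**Working it through.** **1. The plan's own figure.** The sample-size paragraph (under section 11.2) gives 50 analyzable patients for a CCC of 0.60 under H0 and 0.81 under H1, 90% power and a 5% significance level, read as a one-sided z test. With the z-transformation, n = ((1.645 + 1.282) / (atanh 0.81 − atanh 0.60))² + k, where k is 2 or 3 depending on the variance used.

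- atanh 0.81 − atanh 0.60 = 0.4339
- (2.927 / 0.4339)² = 45.5, so n = 48 (k = 2) or 49 (k = 3)
- power at n = 50 is 91.3% or 90.8%

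The stated 50 is reproduced. Nothing below changes an input to it.

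**2. The signals side by side.**

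| Signal | Complete test (2.1) | Cardiorespiratory test (2.1) | Study recording (7) |
|---|---|---|---|
| EEG | yes | not listed | not listed |
| Eye movements | yes | not listed | not listed |
| Muscle tone | yes | not listed | not listed |
| Nasal or oro-nasal, thoracic, abdominal respiration | yes | yes | yes |
| Body position, oximetry, ECG | yes | yes | yes |
| Snoring | not listed | not listed | yes |

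Apart from snoring, the study recording matches the cardiorespiratory column. Section 7 also uses that name for it.

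**3. What a shared time base would do.** The protocol gives neither the share of recording time spent asleep (f) nor the denominator. Assume f of 0.7 to 0.9 and a recording-time denominator. Then AHI per recorded hour = AHI per hour of sleep × f.

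| AHI per hour of sleep | f = 0.7 | f = 0.8 | f = 0.9 |
|---|---|---|---|
| 15 | 10.5 | 12.0 | 13.5 |
| 30 | 21 | 24 | 27 |

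**4. Why the planned analyses would not show it.** CCC = 2·cov(X,Y) / (var X + var Y + (mean X − mean Y)²). If both readings are multiplied by the same constant f, numerator and denominator are both multiplied by f², so the CCC is unchanged. Each Bland-Altman difference is multiplied by f, so a shared shift does not appear as bias between the devices.

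**5. Illustration with f varying between patients.** None of these inputs is in the protocol. Assume AHI per hour of sleep is lognormal with median 15 and log-SD 0.9. Let f have mean 0.9, 0.8 or 0.7 and SD 0.1, and let the time base be the only difference between the EEG-free reference and an EEG-based AHI. Device error is random and set to give a CCC of 0.81 against the study reference.

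| Mean f | Mean AHI understated by | CCC, study reference vs EEG-based AHI | CCC, device vs EEG-based AHI |
|---|---|---|---|
| 0.9 | about 11% | 0.98 | 0.81 |
| 0.8 | about 20% | 0.95 | 0.80 |
| 0.7 | about 30% | 0.89 | 0.77 |

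The level of AHI moves noticeably and the CCC only modestly. The understatement is essentially 1 − f, so it restates the assumption and does not estimate anything.

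**The case against.** The strongest reply is that nothing is hidden. Section 2.1 calls the reduced test a form of polysomnography, section 3 says the device is for full cardiorespiratory monitoring, and the synopsis and section 7 list the signals. This stands. The fault is one of label and scope, not a concealed substitution. The documents also do not say which form of polysomnography is the gold standard, so ranking the EEG form as the only one would need outside sources. The point here is only that the label is unqualified where the protocol itself recognises two tests.

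It also stands that the paired comparison is sound for what it compares: simultaneous recording, the same software, and a corrector blinded to device and subject (section 11.4). In the illustration the CCC against an EEG-based AHI stays well above the null value of 0.60. Mean and minimum SaO₂, heart rate and the position percentages are not rates of events per hour of sleep.

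Three stronger readings are tempting but not supported:

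- A reader might infer that section 5.1 claims validity for sleep disorders in general. There the phrase describes the subjects, the objective is limited to OSA parameters, and section 6.2 requires suspicion of a sleep breathing disorder. The looser phrase about respiratory and sleep disorders in sections 4 and 7 describes indices that are all respiratory, oximetric, cardiac or positional.
- A reader might infer that AHI is per recorded hour. No section says so, and manual correction might or might not remove wake periods.
- A reader might add that events ending in arousal without desaturation are missed. That rests on scoring rules the protocol does not give.

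**Conclusion.** The point holds as a fault of labelling and scope. By the protocol's own distinction the reference is home cardiorespiratory polysomnography with no EEG, eye-movement or muscle-tone signal listed. The trial can support agreement of SOUNDI with that method on the listed indices. It cannot support an unqualified statement of agreement with the gold standard, because agreement with complete polysomnography is not tested.

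A reader might go further and conclude that the validation fails. The documents do not support that: the comparison answers the narrower question properly and the sample size is adequate on its stated inputs.

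The possible shared error in AHI cannot be sized from the protocol. The 10-30% shift depends wholly on an assumed sleep share of 70-90% and an assumed recording-time denominator. What is certain is that the planned analyses would not show such a shift, that the denominator is unstated, and that the sleep-time validity rule cannot be applied with the listed signals.

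**What to change.** - In the synopsis and sections 4, 5.1, 9.1 and 11.1, name the reference as *home cardiorespiratory polysomnography (Embletta, no EEG)* and remove the unqualified gold-standard label.
- Limit the primary conclusion to agreement with that method on the sleep-breathing indices listed in section 7.
- State the time denominator used for AHI and ODI, the same for both devices, and whether manual correction removes presumed wake time from it.
- Reconcile section 7.1 with section 11.3, so that validity rests on a duration the recorded signals can provide.

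This is an amendment of wording. It needs no added patients, signals or procedures and leaves the sample size at 50. The price is a narrower and less favourable performance claim.
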